#### **4.1 Statistical Tests**

Within-participant comparisons (e.g., between pregnant versus non-pregnant conditions or second versus third trimester) will be performed for continuous outcome measures using the Wilcoxon signed rank test and for dichotomous outcome measures using McNemar's test. If the statisticians determine there are not enough women with PK data available at both time points for a meaningful comparison, then no p-value will be calculated. In addition, if there are no discordant pairs for McNemar's test, then the test will not be performed. Between-participant comparisons will be performed for continuous outcome measures using the Wilcoxon rank sum test and for dichotomous outcome measures using the chi-square or Fisher exact test.

90% confidence limits for the geometric mean ratio of the PK exposure parameter in the pregnant versus non-pregnant conditions will also be calculated to describe the range of values that are consistent with the observed data and help the Protocol Team assess whether there is a clinically important difference in exposure in the two conditions. The confidence coefficient will be 90% rather than 95% to match the usual practice in the pharmacokinetic literature to show that two conditions are sufficiently similar (e.g, bioequivalence testing).

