## 2.3 Study Objectives and Outcome Measures

This Primary SAP addresses the following primary and secondary objectives in the study protocol. Some secondary objectives were intended to be exploratory, and will be considered as “Other study objectives”. Therefore, this SAP will not include the outcome measures/analysis contents related to these exploratory objectives (see Section 2.3.2).

The study objectives below will be analyzed under an equivalence framework, including the comparisons between antepartum and postpartum PK parameters. The final analysis for each study arm will be done once the last participant for that arm has completed the last study visit and all queries have been resolved.

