#### 2.3.1.1 (For arms in the ARVs without TB Treatment study arm group)

Objective:

To describe the pharmacokinetic parameters during pregnancy of selected ARV drugs currently used in the clinical care of HIV-infected pregnant women, and to compare these parameters to a) historical pharmacokinetic data from non-pregnant women and b) postpartum pharmacokinetic data from the same women in the study cohorts.

Outcome measure: a) # of women who met area under the curve (AUC) target of ARVs in 2nd trimester (2T), 3rd trimester (3T) and postpartum (PP) (see PK target in Protocol Appendix V); b) AUC, Cmax and Ctrough of ARVs in 2T, 3T and PP

**2.3.1.2 (For arms in the ARVs with First Line TB Treatment arms or No ARVs with First Line TB Treatment study arm groups)**

Objective:

To describe the pharmacokinetic parameters during pregnancy and postpartum of selected ARV drugs (efavirenz, lopinavir/ritonavir) and first line TB drugs when co-administered as part of clinical care of HIV-infected pregnant women and of first line TB drugs when used in HIV-uninfected pregnant women.

Outcome measure: a) # of women who met the AUC target for ARVs and the  $C_{max}$  target for first line TB drugs in 2T, 3T and PP (see PK targets in Protocol Appendix V); b) ARV and first line TB drug AUC,  $C_{max}$  and  $C_{trough}$  in 2T, 3T and PP

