
*Stage 1 analysis for the TB drugs will not be done in real time and will only be done when batched PK data are available (unlike the Stage I analysis for ARVs).  **This comparison may have a smaller sample size than 25 because some women may complete their TB treatment before the postpartum PK visit.  #Interim AUC monitoring (Stage 1 analysis) is not done for these arms (only done during pregnancy).
			

In Stage 1, an individual woman’s PK exposure parameter during pregnancy will be compared in real time to the 10th percentile for that PK exposure parameter for that drug from a non-pregnant population, and the woman and her clinical provider will be notified if the woman’s value is below the 10th percentile. If there is strong evidence that the true percentage of pregnant women having the PK exposure parameter below the 10th percentile for the non-pregnant population is greater than 10%, the study team will evaluate whether to stop enrollment early and whether to recommend that additional study of the drug/drug combination is necessary.

Stage 2 for the ARV drugs taken during pregnancy will implement a repeated measures design, in which antepartum and postpartum measurements from each woman will be compared. This stage requires a minimum of 12 participants in each arm to have postpartum PK measurements. If less than 12 participants out of the 25 in any arm have postpartum measurements, more participants will be enrolled in that arm until the minimum postpartum measurement number of 12

is reached. The comparisons will be made at the within-participant level, using the Wilcoxon signed rank test to assess whether there is a statistically significant difference in the PK exposure parameter in the pregnant versus non-pregnant conditions. 90% confidence limits for the geometric mean ratio of the PK exposure parameter in the pregnant versus non-pregnant conditions will also be calculated to describe the range of values that are consistent with the observed data and help the Protocol Team assess whether there is a clinically important difference in exposure in the pregnant versus non-pregnant conditions.

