## 5 Report Contents

Detailed descriptions of the content of each of the following sections are given in the AIP.

- 1) Maternal demographics summary
  - Race, ethnicity, and country
  - Age, gestational age, weeks after delivery and weight at PK visits
  - ARV/TB medication duration before antepartum visits; concomitant ARV/TB medications at antepartum visits
  - Viral load and CD4 at antepartum, delivery and postpartum visits
- 2) Maternal safety
  - List of AEs reported to Division of AIDS (DAIDS) as Expedited Adverse Events (EAEs)
  - List of Grade 3 or greater AEs
  - List of AEs that are possibly/probably/definitely related to study drugs, as determined by the Core Protocol Team and/or site investigators.
- 3) Maternal PK analysis (as applicable to study arm being analyzed)
  - PK descriptive summaries by parameter and study visit
  - PK parameter comparisons of antepartum vs. postpartum
  - Summary of mothers with AUC above 10th percentile in antepartum vs. postpartum
  - Summary of cord blood/maternal plasma ratio
- 4) Infant demographics
  - Birth weight, length, gestational age and most definitive HIV status
- 5) Infant safety
  - List of congenital anomalies
  - List of AEs reported to DAIDS as EAEs
  - List of Grade 3 or greater AEs
  - List of AEs that are possibly/probably/definitely related to study drugs, as determined by the Core Protocol Team and/or site investigators.
- 6) Infant PK analysis
  - Washout concentration and half-life summary

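### Antepartum versus postpartum target attainment (primary outcome a) has only a McNemar p-value and no interval, so a non-significant or omitted test says little about similarity

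*SAP*

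**What the plan says.** SAP 2.3.1.1 lists as outcome (a) the number "of women who met area under the curve (AUC) target of ARVs in" the second trimester (2T), third trimester (3T) and postpartum (PP). SAP 2.3.1.2 does the same for the first line TB groups, with a Cmax target for the TB drugs. Outcome (b) in both sections is the continuous parameters. The second line TB and contraceptive groups have no outcome of type (a).

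SAP 2.3 sets the frame: "The study objectives below will be analyzed under an equivalence framework, including the comparisons between antepartum and postpartum PK parameters". No margin is given.

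SAP 4.1 assigns the within-woman method "for dichotomous outcome measures using McNemar's test". It does not say whether the exact or the chi-square form is meant and gives no significance level. It lets the statisticians withhold a p-value when too few women have both visits, and continues: "In addition, if there are no discordant pairs for McNemar's test, then the test will not be performed". The 90% confidence limits in 4 and 4.1 are for the GMR only.

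For ARVs in pregnancy, section 4 says of Stage 2: "This stage requires a minimum of 12 participants in each arm to have postpartum PK measurements". The enrolment target is 25. Section 5 lists a summary of mothers with AUC above the 10th "percentile in antepartum vs. postpartum".

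**The concern.** McNemar's test uses only women whose status changes between visits. When most women meet the target at both visits there are few of these, and the test has little to work with. A non-significant result is then likely whether or not pregnancy lowers attainment. When nobody changes status, which is the result closest to similarity, the plan supplies no inferential summary at all.

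Outcome (b) does not have this gap. Its 90% interval shows which differences remain compatible with the data, which is what a plan framed around equivalence needs. Outcome (a) is listed at the same level and has only a test of difference. At stake is whether a reader can tell that attainment was similar, or only that the arm was too small to say.

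**Working it through.** **The SAP's own figure.** SAP 2.5 gives exact 80% limits for 6 of 25. Clopper-Pearson: lower = Beta(0.10; 6, 20) = 0.131, upper = Beta(0.90; 7, 19) = 0.383. This reproduces (0.13, 0.38).

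**Inputs**
- Pairs: 12 (SAP 4, stated for ARVs) and 25 (SAP 2.4).
- Postpartum attainment 90%: an assumption. It follows if the target is the non-pregnant 10th percentile and postpartum women resemble that population. The targets are in Protocol Appendix V, which was not available.
- Antepartum attainment 76%: 1 − 6/25, from the SAP 2.5 alert. Values of 70%, 60% and 50% are an assumed range.
- Two-sided level 0.05: an assumption, with 0.10 as a sensitivity check.
- Dependence between visits: from all changes in one direction (nested) to independent visits. Latent correlations of 0.5 and 0.7 were also tried.

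**What the test needs.** With d discordant women all changing in the same direction, the exact p is 2 × 0.5^d (capped at 1): 1, 0.5, 0.25, 0.125, 0.0625 and 0.031 for d = 1 to 6. The exact test therefore needs at least 6. The uncorrected chi-square statistic is (b − c)²/(b + c), which equals d here, so it needs 4 (p = 0.046).

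**How many are expected with no pregnancy effect.** At 90% for both visits, the discordant fraction is 2 × 0.9 × 0.1 = 0.18 if visits are independent, and about 0.106 at latent correlation 0.7. That is 1.3 to 2.2 women of 12, or 2.7 to 4.5 of 25.

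**Power for 90% to 76%**
- Nested: the number discordant is Binomial(n, 0.14). At n = 25, P(at least 6) = 12.7% and P(at least 4) = 47.1%. At n = 12 these are 0.3% and 7.5%.
- Independent: probability of low antepartum only = 0.24 × 0.90 = 0.216; of low postpartum only = 0.10 × 0.76 = 0.076. Enumerating all splits gives 13.5% (exact) and 23.3% (chi-square) at n = 25, and 1.6% and 12.0% at n = 12.

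Ranges over the dependence assumptions:

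| True antepartum attainment | 12 pairs, exact | 12 pairs, chi-square | 25 pairs, exact | 25 pairs, chi-square |
|---|---|---|---|---|
| 76% | 0.3–2% | 8–12% | 13–14% | 23–47% |
| 70% | 2–4% | 21–22% | 28–38% | 39–77% |
| 60% | 12–15% | 38–51% | 57–81% | 68–97% |
| 50% | 32–33% | 56–77% | 82–97% | 88–99.8% |

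**Sensitivity, 14-point fall, 25 pairs.** At level 0.10: 22–27% (exact) and 36–70% (chi-square). The reference rate matters less. Nested power depends only on the size of the fall. With independent visits at level 0.05, a fall from 80% to 66% gives 12% (exact) and 17% (chi-square).

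**What an interval would show** (Newcombe paired, 90%)
- 12 pairs, 8 meeting the target at both visits and 4 postpartum only: difference 4/12 = 33 points, interval 8 to 57; exact p = 0.125.
- 12 pairs, all meeting the target at both visits: the Wilson lower limit for 12/12 is 12/(12 + 1.645²) = 0.816, so the interval is about −18 to +18 points. The SAP would report no test.
- 25 pairs, all meeting the target: 25/(25 + 1.645²) = 0.902, so about −10 to +10 points.

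**The case against.** The strongest reply is that attainment is a cut of a parameter the SAP also analyses continuously in the same women, by signed-rank test and 90% GMR interval. Under a latent-normal model with 24% low antepartum and 10% postpartum, simulated signed-rank power at correlations 0, 0.5 and 0.7 is about 48%, 77% and 93% with 25 pairs, and 23%, 40% and 61% with 12. Stage 1 also acts on six low women whatever McNemar shows, and its 6 of 25 is a one-sample alert, not a paired effect size. This stands: the plan as a whole is not blind to reduced exposure. But a mean ratio does not show how many women drop below target, and Stage 1 makes no comparison with the same women postpartum.

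Three stronger readings are tempting and are not supported:
- A reader might infer that the SAP would take a non-significant McNemar result as no change. It never says so. Similarity is tied to the GMR interval, SAP 2.2 records no hypothesis, and p-values may be withheld when pairs are few.
- A reader might infer that the test misses most relevant falls throughout 12 to 25 pairs. At 25 pairs a 30-point fall is detected 57–97% of the time and a 40-point fall at least 82%. The SAP names no relevant fall.
- A reader might infer that the chi-square form is badly anti-conservative. Its error is 12.5% conditional on exactly 4 discordant pairs, but unconditionally at most about 4.7% when 10% are low at both visits.

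Skipping McNemar with no discordant pairs is not itself an error, since the statistic is then undefined, and the counts are still reported. The gap is that nothing replaces it. Finally, Appendix V, the protocol's statistical section and the AIP that SAP 5 cites were not available, so the statement that McNemar is the only method is about the SAP text alone.

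**Conclusion.** The point holds within limits. For the two arm groups with outcome (a), the SAP's only within-woman inference on attainment is a McNemar p-value, and there is none when no pair is discordant. For a fall the size of the SAP's own alert proportion, power at 0.05 is below one half at 25 pairs in every case tried and about 12% or less at 12 pairs. A non-significant or omitted test is therefore uninformative about similarity of attainment. First line TB drugs have no stated minimum number of pairs, so they could do worse.

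This rests on 90% postpartum attainment, a two-sided 0.05 level and the dependence range above. At a 0.10 level, the chi-square form with all changes in one direction reaches 70% at 25 pairs, so the statement about power depends partly on choices the SAP leaves open. The missing interval does not depend on them. This is a gap in reporting one primary outcome. It does not invalidate the exposure analysis.

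**What to change.** In SAP 4.1, for 2T versus PP and 3T versus PP attainment in the ARV-without-TB and first line TB groups:
- Make the main result the paired difference in the proportion meeting the target, with a 90% interval from a small-sample paired method such as Newcombe's.
- Report it with the 2x2 paired counts in every arm that has pairs, including when none is discordant.
- If a p-value is kept, name the exact or mid-p McNemar test and the significance level.
- State that a non-significant or omitted test does not support a conclusion of similar attainment.

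The cost is a short SAP edit and a few lines of code per arm, with no new data. The drawback is that intervals will be wide, about 18 points either side of zero for 12 pairs all meeting the target. That width is the information the p-value leaves out.

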#### **4.2 Limitation**

The P1026s study design is opportunistic in that it enrolls women who are already receiving the study drugs as part of clinical care, but this design has one major limitation, namely that the results may be overly optimistic. Since participants must have been stable on the ARV drug/drug combination and/or TB drug combination for at least two weeks prior to PK sampling in order to enroll in the study, the study population will not include women who started the study drug and discontinued it within two weeks due to toxicity, intolerance, virologic failure, or any other reason. Thus, this study will not be able to identify pharmacokinetic, safety, or tolerance issues that occur very soon after drug initiation and estimates of the frequency of outcomes such as virologic response and mother-to-child HIV transmission may be overly optimistic. The fact that the results

of this study will generalize only to the population of women who are able to stay on the study drugs for at least two weeks will be discussed as a limitation of the study in presentations and publications of results. The Protocol Team acknowledges this limitation, but feels that the PK data obtained using the current design will still be quite valuable nonetheless.

## 5 Report Contents

Detailed descriptions of the content of each of the following sections are given in the AIP.

- 1) Maternal demographics summary
  - Race, ethnicity, and country
  - Age, gestational age, weeks after delivery and weight at PK visits
  - ARV/TB medication duration before antepartum visits; concomitant ARV/TB medications at antepartum visits
  - Viral load and CD4 at antepartum, delivery and postpartum visits
- 2) Maternal safety
  - List of AEs reported to Division of AIDS (DAIDS) as Expedited Adverse Events (EAEs)
  - List of Grade 3 or greater AEs
  - List of AEs that are possibly/probably/definitely related to study drugs, as determined by the Core Protocol Team and/or site investigators.
- 3) Maternal PK analysis (as applicable to study arm being analyzed)
  - PK descriptive summaries by parameter and study visit
  - PK parameter comparisons of antepartum vs. postpartum
  - Summary of mothers with AUC above 10th percentile in antepartum vs. postpartum
  - Summary of cord blood/maternal plasma ratio
- 4) Infant demographics
  - Birth weight, length, gestational age and most definitive HIV status
- 5) Infant safety
  - List of congenital anomalies
  - List of AEs reported to DAIDS as EAEs
  - List of Grade 3 or greater AEs
  - List of AEs that are possibly/probably/definitely related to study drugs, as determined by the Core Protocol Team and/or site investigators.
- 6) Infant PK analysis
  - Washout concentration and half-life summary
